6.13.3. Deaths, Other Serious Adverse Events, and Other Notable Adverse Events

The number and percentage of patients who reported a SAE (including those resulting in death) during the safety analysis treatment periods will be summarized by weight/treatment dose group using MedDRA PT nested within SOC. Events will be ordered by decreasing frequency within SOC. A listing of SAEs will be provided.

The number and percentage of patients who permanently discontinued from study treatment due to an AE (including AEs that led to death) during each period will be summarized by weight/treatment dose group using MedDRA PT nested within SOC. Events will be ordered by decreasing frequency within SOC.

6.13.4. Clinical Laboratory Evaluation

As described more fully in compound level safety standards and in the laboratory-related PhUSE white papers [PhUSE 2015], the clinical laboratory evaluations will be summarized by weight/treatment dose group with the following displays:

- Box plots of observed values (and change from baseline values) by visit.
- Change from baseline to last observation will be summarized within the box plot of changes (rightmost column), and descriptive summary statistics will be included in a table below the box plot as described in Section 6.1.3.
- Treatment emergent abnormal high lab values (ie, patients shifting from a normal/low maximum baseline value to a high maximum post-baseline value) or low lab values (ie, patients shifting from normal/high minimum baseline value to a low minimum postbaseline value).
- Scatter plot of maximum (minimum) postbaseline value versus maximum (minimum) baseline value.
- Shift tables showing the number of patients who shift from each category of maximum (minimum) baseline observation to each category of maximum (minimum) postbaseline observation. Here categories may be low, normal, or high with cut-offs defined in the compound level safety standards.

For these displays, the postbaseline period for continuous variables will be the combined Induction and Maintenance period and for categorical variables will be the Induction period and the combined Induction and Maintenance period. Postbaseline measurement for continuous analysis (eg, boxplots) will include *only* scheduled measurements, while postbaseline categorical analysis (eg, shifts) will include *both* scheduled and unscheduled measurements.

Measurements are defined to be in the baseline periods as follows:

- for analyses of continuous measurements: the last scheduled or unscheduled nonmissing measurement recorded during the Screening Period, and
- for analyses of categorical measurements: all scheduled or unscheduled nonmissing measurements recorded during the Screening Period.

For any lab performed on the day of first taking study medication at the start of the postbaseline period, the start time of the study treatment will be used to determine whether the lab was pre versus postbaseline. If time for the lab is missing, it will be assumed to be in the baseline period (ie, we assume the protocol defined order of procedures was followed). Following the compound level safety standards, for some labs a safety concern may exist for only high (or only low) values. For these labs, displays with only maximum (or minimum) values will be used and shift tables will be presented accordingly.

6.13.5. Vital Signs and Other Physical Findings

As described more fully in compound level safety standards and in the vital signs-related PhUSE white papers [PhUSE 2013], vital signs will be summarized similarly to the clinical laboratory evaluation (see Section 6.13.4). For vital signs, the low and high limits are based on a combination of a specified value and a change or percentage change by age, as shown in Table AMBU.6.7. In this case, the PhUSE white paper recommends providing scatter plots and shifts to low/high. Boxplots will also be presented.

Table AMBU.6.7. Categorical Criteria for Abnormal Treatment-Emergent Blood Pressure and Pulse Measurement for Children by Age Group

Age at IC (years)		Systolic BP mm HG	Diastolic BP mm HG	Pulse/HR bpm
≥2 and <5	Low	≤75 and DFB ≥15	≤40 and DFB ≥10	≤60 and DFB ≥25
	Higha	≥110 and IFB ≥15	≥76 and IFB ≥10	>160 and IFB ≥25
≥5 and <10	Low	≤80 and DFB ≥15	≤45 and DFB ≥10	≤60 and DFB ≥25
	Higha	≥119 and IFB ≥15	≥78 and IFB ≥10	>150 and IFB ≥25
≥10 and <13	Low	≤85 and DFB ≥20	≤50 and DFB ≥10	≤60 and DFB ≥25
	High ^a	≥126 and IFB ≥20	≥82 and IFB ≥10	>140 and IFB ≥25
≥13 and <18	Low	≤90 and DFB ≥20	≤50 and DFB ≥10	≤50 and DFB ≥15
	Higha	≥129 and IFB ≥20	≥86 and IFB ≥10	>120 and IFB ≥15

Abbreviations: BP = blood pressure; HR = heart rate; DFB = decrease from baseline; IFB = increase from baseline; IC = Informed Consent.

^a The high limit values shown in this table correspond to the 95th percentile for the age group under the 2017 ACC/AHA Task Force on Clinical Practice Guidelines revised criteria for hypertension. Values higher than the 95th percentile are consistent with Stage 1 or Stage 2 hypertension. Under some circumstances it may be appropriate to conduct analyses considering only the change from baseline reference limit.

6.13.6. Electrocardiograms

Complete electrocardiogram (ECG) data will not be part of the clinical database for the individual studies. Any clinically significant findings from ECGs that result in a diagnosis and that occur after the patient receives the first dose of the investigational treatment will be reported to Lilly or its designee as an AE via eCRF. Aside from standard AE summary tables no additional analysis of ECG data will be performed.

6.13.7. Adverse Events of Special Interest

This section includes areas of interest whether due to observed safety findings, potential findings based on drug class, or safety topics anticipated to be requested by a regulatory agency for any reason. In general, potential adverse events of special interest (AESI) relevant to these special safety topics will be identified by one or more standardized MedDRA query(ies) (SMQs), by a Lilly defined MedDRA PT listing based upon the review of the most current MedDRA version, or by treatment emergent relevant laboratory changes, as described below. Additional special safety topics may be added as warranted.

Unless otherwise specified, the AESIs will be summarized by weight/treatment dose group for the safety population during the Induction and combined Induction and Maintenance periods using the baseline and postbaseline definitions described in Section 6.13.2.

Full details of the search terms and rules for deriving AESIs in each of the sections below are described in the compound level safety standards along with information about the types of summaries and listings to be provided.

6.13.8. Immunogenicity

An individual sample is potentially examined multiple times in a hierarchical procedure to produce a sample anti-drug antibody (ADA) assay result and potentially a sample neutralizing anti-drug antibodies assay result. A patient has treatment-emergent anti-drug antibodies (TE ADA) when ADAs are induced or boosted by exposure to study drug. That is, when at least one postbaseline ADAs sample has a 4-fold increase in titers compared to baseline (if ADA were present at baseline) or has a titer 2-fold greater than the minimum required dilution of 1:10 (if no ADAs were present at baseline). Compound level safety standards will be followed in the analyses of immunogenicity. Listings of immunogenicity assessments will be provided along with the summary of specified TEAEs by TE ADA status. The summary of TE ADA and neutralizing anti-drug antibodies status will be produced. Analyses of the relationship between immunogenicity and PK will be conducted as part of the PK/PD analyses as described in Section 6.11.1. Additional assessments of the relationship between immunogenicity and efficacy will be performed as deemed appropriate.

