
 To evaluate histologic-endoscopic mucosal remission following mirikizumab treatment at Week 12 or Week 52 	
 Proportion of patients with histologic-endoscopic mucosal remission at Week 12 Proportion of patients with histologic-endoscopic mucosal remission at Week 52 
Histologic-endoscopic mucosal remission is defined as achieving both histologic remission and endoscopic remission. Histologic remission will be defined in the SAP.

Objectives	Endpoints

 To evaluate the development of anti-mirikizumab antibodies and their effect on efficacy, safety, and mirikizumab exposure 	
 Proportion of patients who have treatment-emergent anti-drug antibodies (TEADA) Relationship between TEADA and efficacy Relationship between TEADA and safety Relationship between TEADA and mirikizumab PK

 CCI [REDACTED] 	
 CCI [REDACTED]

Abbreviations: NRS = numeric rating scale; PUCAI = Pediatric Ulcerative Colitis Activity Index; SAP = statistical analysis plan.

Summary of Study Design:

Study AMBU is a multicenter, Phase 2, open-label study designed to evaluate the safety, PK, PD, and clinical response of mirikizumab in pediatric patients, and to provide data for dose confirmation for Phase 3. The study population includes pediatric patients with moderately to severely active UC, who have an inadequate response to, loss of response to, or are intolerant to non-biologic therapy for UC (biologic-naive), and/or those who have been exposed to at least 1 biologic and/or Janus kinase (JAK) inhibitor therapy for UC (biologic/JAK inhibitor-experienced).

Treatment Arms and Duration:

Patients weighing >40 kg will receive a mirikizumab induction dose of 300 mg via intravenous (IV) infusion and patients weighing ≤40 kg will receive 5 or 10 mg/kg via IV infusion at Weeks 0, 4, and 8. Patients who have met the clinical response criteria at Week 12 will receive subcutaneous (SC) maintenance doses of 200 mg (weight >40 kg), or 100 mg (weight >20 kg to ≤40 kg), or 50 mg (weight ≤20 kg) every 4 weeks (Q4W) from Weeks 12 to 48. Patients who have not achieved clinical response at Week 12 may receive extended induction at the next higher dose, or will be discontinued. In cases where there is no higher dose, patients may receive extended induction dosing at the current dose.

Number of Patients:

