9.4.4. Immunogenicity Assessments

At the visits and times specified in the Schedule of Activities (Section 2), venous blood samples will be collected to determine antibody production against mirikizumab.

- Pre-dose samples will be obtained per the Schedule of Activities.
- The actual date and time (24-hour clock time) of each sample collection will be recorded.

To aid interpretation of these results, a pre-dose blood sample for PK analysis will be collected at the same time points.

In the event of a systemic allergic/hypersensitivity reaction (Section 9.2.2.2), additional blood samples will be obtained as specified in the Schedule of Activities (Section 2).

Sample collection, handling, and use

Instructions for the collection and handling of blood samples will be provided by the sponsor.

Immunogenicity will be assessed by a validated assay designed to detect ADAs in the presence of mirikizumab at a laboratory approved by the sponsor. Antibodies will be further evaluated for their ability to neutralize the activity of mirikizumab.

Sample retention

Samples will be retained for a maximum of CCI after the last patient visit, or for a shorter period if local regulations and ERBs allow, at a facility selected by the sponsor. The duration allows the sponsor to respond to future regulatory requests related to mirikizumab. Any samples remaining after CCI will be destroyed.

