Appendix 2. Clinical Laboratory Tests

CCI

Selected tests may be obtained in the event of systemic allergic/hypersensitivity events.

Hypersensitivity Tests^a

[figure not shown]
Immunogenicity testing (ADA)	Tryptase
Serum mirikizumab concentration (PK)	Complement
	Cytokine Panel

Abbreviations: ADA = anti-drug antibody; PK = pharmacokinetics.

^a Assayed by Lilly-designated laboratory and for immediate hypersensitivity events only.

Laboratory Test Prioritization

Care should be taken to safeguard study participants with regard to the amount of blood drawn for study procedures. All efforts have been made to minimize required sampling in this protocol; however, in the case of younger and lower body weight patients, the following guidance is provided. Importantly, sites should follow local institutional review board guidelines, where applicable. Patients **CCI** old with body weight lower than **CCI** will require reduced blood volume collection, and some tests will need to be excluded. In the situation where blood volume is limited and all tubes cannot be collected, the following sample tubes should be removed in this order:

Please refer to the lab manual for collection tube volumes for each of the above mentioned tests.

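### The adverse-event table by anti-drug-antibody status ignores whether the event came before the antibody, and unequal sampling can bias it in either direction.

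*SAP*

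**What the plan says.** The protocol synopsis lists "Relationship between TEADA and safety" among the secondary endpoints, and Protocol 10.3.6 says that the relationship will be assessed.

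SAP 6.13.8 defines status per child. If ADA were present at baseline, the child is positive "when at least one postbaseline ADAs sample has a 4-fold increase in titers compared to baseline". If not, one post-baseline titer 2-fold above the minimum required dilution of 1:10 is enough. The section names no time window and does not limit the samples to scheduled ones. The safety display is a single sentence: "Listings of immunogenicity assessments will be provided along with the summary of specified TEAEs by TE ADA status". The section adds: "Compound level safety standards will be followed in the analyses of immunogenicity". SAP 6.13.2 has AE tables show numbers and percentages of patients, not rates.

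Three protocol rules affect who is sampled, and when:

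- **Protocol 9.4.4:** "In the event of a systemic allergic/hypersensitivity reaction (Section 9.2.2.2), additional blood samples will be obtained as specified in the Schedule of Activities".
- **Protocol Appendix 2** puts ADA among the hypersensitivity tests, with the footnote "Assayed by Lilly-designated laboratory and for immediate hypersensitivity events only".
- **Protocol 8.1.1** has study drug stopped after a systemic hypersensitivity event or anaphylaxis.

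**The concern.** The table will be read as an answer to whether antibodies raise the risk of reactions. An ever-positive label is fixed by what happens over the whole study and then applied back to its start. All three scheduled induction infusions (Weeks 0, 4 and 8) come before Week 12. A reaction to one of them in a child first positive at Week 12 or later is counted as an event with antibody present, although none had been detected. For an immediate reaction to the Week 0 infusion, a treatment-emergent antibody cannot be the cause.

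The groups are also not sampled or followed equally. A child with an immediate hypersensitivity reaction gets extra chances to test positive. A child who leaves early has fewer samples and less time for events. A child whose drug is stopped after a systemic reaction may lose later samples. Protocol 3.3 treats immediate hypersensitivity reactions as adverse drug reactions and mentions two reports consistent with anaphylaxis, so this is where a misleading table would matter most.

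**Working it through.** The plan gives no figure for this analysis, so there is nothing to reproduce. The check asks what the planned table would show if antibodies and reactions were unrelated. The measure is the risk ratio (RR): the risk of a reaction in TE ADA positive children divided by the risk in TE ADA negative children.

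**Inputs.** From the documents: the any-sample definition, event-triggered ADA samples, drug stopped after a systemic reaction, and about 30 children (SAP 5.2: 10 above 40 kg and 20 at or below). Assumed, because they are redacted or not stated: the number of scheduled ADA samples K, extra samples per reaction E, positivity per sample p, reaction risk, and dropout.

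**1. Extra samples alone.** P(positive) = 1 − (1 − p)^(K+E) in children with a reaction and 1 − (1 − p)^K in the others. Take K = 4, p = 5%, E = 2 and 10% reactions:

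- with a reaction: 1 − 0.95^6 = 0.265; without: 1 − 0.95^4 = 0.185
- risk of reaction if positive: 0.1 × 0.265 / (0.1 × 0.265 + 0.9 × 0.185) = 0.137
- risk of reaction if negative: 0.1 × 0.735 / (0.1 × 0.735 + 0.9 × 0.815) = 0.091
- RR = 0.137 / 0.091 = 1.50

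Over K = 4 and 7, p = 1–10% and E = 1–3, the RR is 1.13 to 1.93.

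**2. Simulation with time.** 2,000,000 children per scenario; samples at assumed Weeks 4, 8, 12, 16, 24, 36 and 52; 15% reactions by Week 52; dropout 0, 20 or 40%; ADA either transient (4% per sample) or persistent (25% by Week 52).

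| Scenario, no true link | Apparent RR |
|---|---|
| No dropout, no extra samples, no stop at the reaction | 0.99–1.00 |
| Dropout 20–40% only | 1.08–1.23 |
| 2–3 extra samples, transient ADA, dropout 0–40% | 1.28–1.71 |
| 1–3 extra samples, persistent ADA, dropout 0–40% | 0.99–1.24 (driven by dropout) |
| Sampling stops at the reaction, no extra samples | 0.39–0.66 |
| Sampling stops at the reaction, 1–3 extra samples | 0.48–1.20 |

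The first row shows that ignoring time order does not by itself distort the ratio when all children are followed and sampled alike. What it distorts is attribution. With no extra samples and no stop at the reaction, 41–58% of reactions in positive children had no earlier positive scheduled sample. For a commoner event (40% of children, persistent ADA) the share was 59–61%.

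**3. Trial size.** At 25% positive, 30 × 0.25 = 7.5 positive children, and 7.5 × 0.15 ≈ 1.1 of them with a reaction. In 20,000 simulated trials of 30 children (transient ADA, 20% dropout), the share with an observed RR of at least 2 was 28% with no extra samples, 37% with two, and 23% with two plus a stop at the reaction. With persistent ADA these shares were 29%, 30% and 13%.

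**4. The remedy.** Treating status as time-varying, with positive time starting at the first positive scheduled sample and events compared per unit of person-time, gave a null rate ratio of 0.99–1.02 in every scenario.

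**The case against.** A reader might infer that the plan will produce a false harm signal. One set of assumptions gives an RR of 1.21: 30% stopping at Week 12, 25% with transient ADA, 0.4 specified TEAEs per patient-year, and two extra samples after any event. The documents do not support that as a prediction:

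- The triggered tests are for immediate hypersensitivity only, so they cannot affect other TEAEs. Even when applied to all events, they move that ratio only from 1.17 to 1.21.
- No stopping rate is given, and Week 12 nonresponders may continue into extended induction.
- Early stoppers have an early termination visit and post-treatment visits, where ADA may be drawn. The ADA row is redacted.
- Stopping drug after a systemic reaction pushes the ratio the other way.

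A reader might also infer that no timing rule exists. That cannot be shown. The SAP defers to compound level safety standards that are not among the documents, and SAP 6.13.7.3 on hypersensitivity appears in the contents, but its text is not in the public copy.

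Finally, the display is descriptive and small, and the planned listings may allow timing to be checked child by child. All of these points stand. They limit the direction, size and weight of the concern. They do not supply the missing rule on time order, or on whether event-triggered samples count, for a listed secondary endpoint.

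**Conclusion.** The concern holds as a minor point. As publicly written, the table credits antibodies with events that came before their detection, and it compares percentages between groups that may be sampled and followed unequally. The bias can run either way. Extra samples inflate the ratio only if positivity is transient or borderline, dropout inflates it modestly, and lost sampling after a reaction can bring it well below 1. Every figure in the check rests on assumed rates and an assumed schedule, so none estimates the bias in this trial. With about one reaction expected among positive children under those assumptions, chance would usually outweigh the bias. In so small a table, the order of event and antibody in each case is the most useful information, and the planned summary does not show it.

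**What to change.** In SAP 6.13.8, or by explicit reference if the compound level standards already say so:

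- In TE ADA positive children, split specified TEAEs into onset before, and onset on or after, the first positive scheduled sample.
- Give patient-years for each segment and for TE ADA negative children, and compare rates. The comparator for positive time should be all time not yet positive: the earlier segment of positive children pooled with the time of negative children. The earlier segment alone is not a fair comparator. If sampling stops at the reaction and there are no extra samples, it contains no reactions by construction.
- Keep event-triggered samples, and show children first positive on one as a separate flagged category. They should neither be dropped nor set the start of positive time. Restricting ever/never status to scheduled samples, with no time split, would discard the sample taken at the reaction and leave the 0.39–0.66 problem in place.
- State that the split is by detection, which may come later than the true onset of antibody.

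The cost is SAP wording and a little programming. Sample dates and times (Protocol 9.4.4), AE start timing (SAP 6.13.2) and patient-years (SAP 6.13.1) are already recorded or planned. The downside is segments with few events and little person-time, which should be presented as description only.

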6.14. Subgroup Analyses

Subgroup analyses may be conducted for secondary endpoints and safety endpoints. Subgroups to be evaluated may include sex, age, race, geographic region, baseline disease severity, duration of disease, previous use of biologic therapy, and any other baseline characteristic subgroups as deemed appropriate.

6.15. Protocol Violations

Protocol deviations will be identified throughout the study. Important protocol deviations (IPDs) are defined as those deviations from the protocol that would potentially compromise patients' safety, data integrity, or study outcome.

A separate document known as the "The AMBU Trial Issues Management Plan" will describe the categories and subcategories of important protocol deviations, and how the IPDs would be identified.

The number and percentage of patients having IPDs will be summarized within category and subcategory of deviations by dosing regimen for the mITT population. A by-patient listing of IPDs will be provided.

6.16. Data Snapshots and Interim Analyses

The planned data snapshot and interim analyses are described as follows.

6.16.1. Data Snapshots

There will be 2 data snapshots taken of PK and safety data:

The first snapshot will be taken when at least 5 patients reach Week 4. This will provide an early assessment of PK and safety data. This analysis is planned to enable dose confirmation for the Phase 3 study for patients >40 kg.

The second snapshot will be taken when approximately 5 patients in the ≤40 kg group (5 mg/kg IV Q4W) reach Week 4. This analysis is planned to enable the enrollment of the 10 mg/kg treatment group.

6.16.2. Interim Analyses

An interim analysis is planned when approximately 15 patients in the \leq 40 kg group reach Week 12. This analysis will allow confirmation of dose for patients \leq 40 kg to begin the Phase 3 study.

Interim analyses provided will include assessments and summaries of disposition, demographics, safety, PK, and efficacy endpoints. Safety analyses will include, but are not limited to summaries of exposure, AEs/SAEs, labs, vitals, AESIs, and immunogenicity and will be performed according as described in Section 6.13. Efficacy analyses will include summaries of MMS clinical remission, response, and the associated component scores at Week 12 and Week 52. Pediatric Ulcerative Colitis Activity Index remission, response, and associated scores will also be summarized at relevant visits. Refer to Section 6.10.1 for details regarding the analysis of each endpoint.

No multiplicity adjustment will be made due to multiple comparisons or due to interim analyses.

Additional data snapshots and/or interim analyses may be performed as deemed necessary, based on emerging data from the ongoing study.

Study sites will receive information about interim results ONLY if it is required for the safety of their patients.

